12.4 General considerations

Demographic and clinical characteristics at baseline, medical history, efficacy and safety data will be summarized using descriptive statistics by treatment group and by time point of assessment.

Continuous data will be summarized in terms of the mean, standard deviation (SD), median, 25th and 75th percentile, minimum, maximum and number of observations. In general, categorical and ordinal data will be summarized in terms of the frequency and percentage in each category.

Using explorative methods, both treatment groups will be analysed for homogeneity on the basis of patient's baseline characteristics. Analysis of variance (ANOVA) or Wilcoxon-Mann-Whitney test, as appropriate, will be used to test and compare the continuous demographic and baseline characteristics between treatment

CONFIDENTIAL Page 64 of 88

groups. The Pearson χ^2 (or Fisher's exact test) will be used to perform between-group comparisons on categorical and binominal demographic and baseline data.

Medical history will be coded using the Medical Dictionary for Regulatory Activities (MedDRA) version 17.1. The prior and concomitant medication will be coded using World Health Organization (WHO) Drug Dictionary (version 2013-12-19), including ATC code.

For the primary efficacy endpoint, the non-inferiority hypothesis will be tested at one-sided 0.05 significance level. For other statistical analyses statistical significance will be declared at the 2-sided 0.05-level, unless otherwise specified.

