12.6 Efficacy evaluation

12.6.1 Efficacy endpoints

Primary endpoint:

• Proportion of patients with clinical success as judged by the investigator at the test of cure visit (Visit 4).

Secondary endpoints:

- Proportion of patients with clinical success as judged by the investigator at the Visit 2 (switch to oral therapy) and Visit 3
- Proportion of patients with infection relapse at Visit 5
- Time to switch therapy from i.v. to oral therapy
- Need for other antibiotic treatment
- Proportion of patients with microbiological responses at the Visit 2 (switch to oral therapy), Visit 3 and Visit 4.

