12.6.3 Secondary efficacy analyses

As a supportive analysis, the primary efficacy endpoint will be analyzed in the CE population using the same method as that used for the primary efficacy analysis.

For secondary efficacy analyses, the clinical success rates of the patients in the mITT and CE populations at Visit 2 (switch to oral therapy) and Visit 3 as well as the number (proportion) of patients who needed other antibiotic treatment (treatment failure) will be analyzed using a two-sided 95% confidence interval (equality test) calculated based on the same statistical test as for the primary analysis.

Additionally, the results of statistical comparison of the clinical success rates using the logistic regression will also be provided.

Time to switch therapy from i.v. to oral therapy will be evaluated using the Kaplan – Meier survival analysis method and compared by log-rank test between treatment groups. The Kaplan-Meier curves will be presented graphically.

Microbiological efficacy endpoints will include microbiological success rates evaluated per each patient and by identified pathogens in b-mITT and BE.

The percentage and the number of patients with microbiological success and failure will be summarized by visit and treatment group. Microbiological success is defined as the assessments of eradication and presumed eradication. Other results of assessments (excluding unevaluable) will be regarded as microbiological failure. The difference between microbiological success rates and its CI will be calculated using the same method as that used for the secondary efficacy endpoints.

The percentage and number of the baseline-identified strains (sputum and blood culture) with microbiological success and failure will be summarized by visit and treatment group. The frequency of each category and sample source (sputum and blood culture) will be presented separately and by treatment group. Microbiological data by identified pathogens will be analyzed descriptively.

Microbiological efficacy evaluation

Based on the results of culture (bacteriological) study the microbiological response will be assessed. Microbiological response is defined as:

- 1. Eradication (admission pathogen[s] is absent),
- 2. Presumed eradication (if no material available for culture because of clinical success)
- 3. Persistence (admission pathogen[s] is present),
- 4. Presumed persistence (no material available for culture for patients with clinical failure),

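### Section 12.4 lets significance be declared at two-sided 0.05 on seven secondary efficacy comparisons with no order, gating, alpha control or exploratory label in the protocol text

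*Combined protocol and SAP*

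**What the plan says.** Section 12.4 sets two levels. For the primary endpoint: "For the primary efficacy endpoint, the non-inferiority hypothesis will be tested at one-sided 0.05 significance level". For the rest: "For other statistical analyses statistical significance will be declared at the 2-sided 0.05-level, unless otherwise specified".

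Section 12.6.1 lists the secondary efficacy endpoints, and section 12.6.3 gives the methods:

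- **Clinical success at Visits 2 and 3, and need for other antibiotics.** These "will be analyzed using a two-sided 95% confidence interval (equality test) calculated based on the same statistical test as for the primary analysis". The success rates are analysed in both mITT and CE. The Synopsis repeats this text.
- **Time to i.v.-to-oral switch.** Kaplan-Meier curves, "compared by log-rank test between treatment groups".
- **Microbiological success by visit, in b-mITT and BE.** "The difference between microbiological success rates and its CI will be calculated using the same method as that used for the secondary efficacy endpoints".
- **Clinical success rates again,** by logistic regression.

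One listed endpoint, "Proportion of patients with infection relapse at Visit 5", has no stated test. Results by pathogen are descriptive.

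The only ordered step is in section 12.6.2: superiority on the primary endpoint is tested only after non-inferiority is shown. Section 12.9 refers to a separate statistical analysis plan, to be finalized before database close-out. Its text is not in the documents.

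**The concern.** The rule in 12.4 is permissive: it says that significance will be declared, test by test. The authors use limiting labels elsewhere. Baseline comparisons are explorative, the CE analysis of the primary endpoint is supportive, and safety and by-pathogen data are descriptive. The secondary efficacy comparisons carry no such label and have no place in any sequence. Nothing makes them depend on the primary result, so a secondary difference could be declared significant even if non-inferiority is not shown.

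Two secondary objectives in section 4.2, efficacy of the intravenous phase and microbiological efficacy, rest on these comparisons. With several chances at 0.05, an isolated finding at one visit or in one population could be reported as a significant advantage or disadvantage of nemonoxacin when it is only chance. What is at stake is how far a secondary result can be claimed, not the primary decision.

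**Working it through.** **The plan's own figure.** There is none to reproduce. The documents give 0.05 per comparison and no family-wise rate.

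**Inputs from the protocol**

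- Level per comparison: 0.05, two-sided (12.4), so the critical value is c = 1.96.
- Comparisons with a stated between-group method (12.6.1 and 12.6.3):

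| Outcome | Count |
|---|---|
| Clinical success, Visits 2 and 3 | 2 |
| Need for other antibiotics | 1 |
| Time to switch (log-rank) | 1 |
| Microbiological success, Visits 2, 3 and 4 | 3 |
| **Total k** | **7** |

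**Input assumed.** The documents give no correlation between the test statistics, so a common correlation ρ is varied from 0 to 0.9.

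**Step 1: independent tests, no true difference anywhere.** The chance of at least one declared difference is 1 − 0.95^k. For k = 7 it is 1 − 0.95^7 = 0.302.

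**Step 2: correlated tests.** For k equally correlated normal statistics, condition on the shared component u:

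FWER = 1 − ∫ φ(u) · [Φ((c − √ρ·u)/√(1−ρ)) − Φ((−c − √ρ·u)/√(1−ρ))]^k du

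Numerical integration for k = 7 gives:

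| ρ | 0 | 0.3 | 0.5 | 0.7 | 0.8 | 0.9 |
|---|---|---|---|---|---|---|
| Chance of at least one | 30.2% | 27.1% | 23.0% | 17.8% | 14.9% | 11.4% |

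Simulation with 400,000 runs agrees for ρ from 0 to 0.8.

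**Step 3: is strong correlation plausible?** The definitions link the outcomes. Additional antimicrobial therapy is itself a criterion of clinical failure (Table 10-1). Presumed eradication and presumed persistence are assigned from the clinical outcome (12.6.3). Clinical response at Visit 2 is assessed on the switch day, and the switch requires clinical stability (9.2.2, Appendix 2). A grouped structure may therefore be more realistic than a common ρ. With the four clinical and switch tests in one group and the three microbiological tests in another, and correlation 0.5 between groups, simulation gives about 18% when the within-group correlation is 0.8 and about 16% when it is 0.9. Both lie inside the range in Step 2.

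**Step 4: sensitivity to the count.** If relapse were also tested, k = 8 gives 33.7% at ρ = 0 and 25.0% at ρ = 0.5. Counting each CE and BE repeat separately, and reading need for other antibiotics as analysed in both mITT and CE, gives 4 + 2 + 1 + 6 = 13 tests. CE and BE are subsets of mITT and b-mITT, so these repeats largely ask the same question again. Seven is used as the main count.

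**The case against.** The strongest reply is that the plan does what it says. It states a level for each analysis and never promises 5% across the family, so a family-wise rate above 5% contradicts nothing. The secondary objectives are worded as evaluation, no secondary success criterion is set, and the only confirmatory objective, primary non-inferiority, is untouched. Multiplicity may also be handled in the separate SAP.

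Much of this stands, and it limits the point. Three stronger readings are tempting and not supported:

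- **That the false-positive rate simply is 23% to 30%.** These figures depend on assumptions about correlation and the number of tests, and the documents give no correlation. With the linked definitions noted above, values well below 23% are plausible.
- **That a promised 5% is broken.** The 0.05 in 12.4 is a level per comparison. Setting a family-wise rate against it compares different quantities.
- **That every secondary efficacy comparison is covered.** Relapse at Visit 5 has no stated test, by-pathogen data are descriptive, and the rule has its own exception for cases specified otherwise.

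The reply does not remove the permission to declare. The protocol text contains no exception for the seven comparisons. What it defers to the SAP is the handling of missing data (12.5) and the detail of the analysis (12.9); multiplicity is not mentioned. Until another text says otherwise, 12.4 governs.

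**Conclusion.** The concern holds for the protocol text. Section 12.4 authorises declarations of significance at two-sided 0.05, and 12.6.3 supplies seven secondary efficacy comparisons to which this applies, with no order, gating, alpha control or exploratory label.

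If there is no true difference on any of the seven, the chance of at least one declared difference is about 11% to 30%. The range rests on the assumed correlation and on counting each outcome once. It is above 5% throughout, but no single value within it can be read from the documents.

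The primary non-inferiority test and the superiority test that follows it are not affected, and no estimate, interval or sample size changes. A reader might infer that the whole plan lacks multiplicity control. That cannot be concluded, because the SAP text is not available. The change is a cheap improvement that limits what may be claimed from secondary results.

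**What to change.** In 12.4, keep the two-sided 0.05 level for the superiority test and, as a nominal level, for the baseline comparisons. Then add:

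> Secondary efficacy comparisons in 12.6.3 are exploratory; they are reported as estimates with nominal two-sided 95% confidence intervals and nominal p-values, not adjusted for multiplicity, and no statistical significance will be declared.

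Make matching changes in 12.6.3, the Synopsis and the SAP before unblinding.

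If the sponsor wants a confirmatory secondary claim, the alternative is a short prespecified sequence in mITT, entered only after primary non-inferiority is shown and stopped at the first non-significant result. That is optional and not needed to close this point.

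The cost is one sentence and its matching edits, with no new patients, data or analyses. The downside is that the sponsor can no longer call an isolated secondary result statistically significant.

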12.5 Procedure for accounting for missing, unused, and spurious data

Procedure for accounting for missing, unused, and spurious data will be described in Statistical Analysis Plan.

12.6 Efficacy evaluation

12.6.1 Efficacy endpoints

Primary endpoint:

• Proportion of patients with clinical success as judged by the investigator at the test of cure visit (Visit 4).

Secondary endpoints:

- Proportion of patients with clinical success as judged by the investigator at the Visit 2 (switch to oral therapy) and Visit 3
- Proportion of patients with infection relapse at Visit 5
- Time to switch therapy from i.v. to oral therapy
- Need for other antibiotic treatment
- Proportion of patients with microbiological responses at the Visit 2 (switch to oral therapy), Visit 3 and Visit 4.

12.6.2 Primary efficacy analysis

The percentage and the number of patients with different categories of clinical response ("clinical success", "clinical failure", "indeterminate") will be summarized by treatment group in mITT and CE populations for Visit 2 (switch to oral therapy), Visit 3 and Visit 4.

The percentage of patients with clinical success (as judged by the investigator) at the test of cure Visit 4 is defined as primary endpoint variable.

In regards to efficacy for CAP, non-inferiority of Nemonoxacin compared to Tavanic[®] will be evaluated for clinical response by using a one-sided 95% confidence interval for the difference in the primary efficacy endpoint (investigational drug minus comparator). Non-inferiority of Nemonoxacin will be stated if the lower boundary of the estimated one-sided 95% confidence interval for the difference in the clinical success rate of Nemonoxacin and Tavanic[®] is above -15% the Farrington-Manning test.

CONFIDENTIAL Page 65 of 88

The primary analysis will be performed in the mITT population.

If non-inferiority is shown, a test on superiority will be performed in addition using the two-sided 95% confidence interval. The test on superiority is significant, if the lower two-sided 95% confidence interval limit is above "0".

12.6.3 Secondary efficacy analyses

As a supportive analysis, the primary efficacy endpoint will be analyzed in the CE population using the same method as that used for the primary efficacy analysis.

For secondary efficacy analyses, the clinical success rates of the patients in the mITT and CE populations at Visit 2 (switch to oral therapy) and Visit 3 as well as the number (proportion) of patients who needed other antibiotic treatment (treatment failure) will be analyzed using a two-sided 95% confidence interval (equality test) calculated based on the same statistical test as for the primary analysis.

Additionally, the results of statistical comparison of the clinical success rates using the logistic regression will also be provided.

Time to switch therapy from i.v. to oral therapy will be evaluated using the Kaplan – Meier survival analysis method and compared by log-rank test between treatment groups. The Kaplan-Meier curves will be presented graphically.

Microbiological efficacy endpoints will include microbiological success rates evaluated per each patient and by identified pathogens in b-mITT and BE.

The percentage and the number of patients with microbiological success and failure will be summarized by visit and treatment group. Microbiological success is defined as the assessments of eradication and presumed eradication. Other results of assessments (excluding unevaluable) will be regarded as microbiological failure. The difference between microbiological success rates and its CI will be calculated using the same method as that used for the secondary efficacy endpoints.

The percentage and number of the baseline-identified strains (sputum and blood culture) with microbiological success and failure will be summarized by visit and treatment group. The frequency of each category and sample source (sputum and blood culture) will be presented separately and by treatment group. Microbiological data by identified pathogens will be analyzed descriptively.

Microbiological efficacy evaluation

Based on the results of culture (bacteriological) study the microbiological response will be assessed. Microbiological response is defined as:

- 1. Eradication (admission pathogen[s] is absent),
- 2. Presumed eradication (if no material available for culture because of clinical success)
- 3. Persistence (admission pathogen[s] is present),
- 4. Presumed persistence (no material available for culture for patients with clinical failure),
- 5. Unevaluable (assessment is not possible because the patient was lost to follow-up after the treatment or posttherapy culture was not obtained).

CONFIDENTIAL Page 66 of 88

6. Superinfection is defined as the appearance of a new pathogen in patients with clinical failure.

The eradicated and presumed eradicated microbiological responses will be combined and classified as microbiological success. Other results of assessments (excluding unevaluable) will be regarded as microbiological failure.

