8.5 Method of Assigning Patients to Treatment Groups

At Visit 1 (Day 1) to minimize or avoid bias randomization will be done. The study will utilize IWRS for randomization of the eligible patients. In accordance with randomization number each patient will be assigned to one of two treatment groups at the ratio of 1:1 (see Table 6-1):

- Investigational drug (Nemonoxacin) group
- Comparator (Tavanic®) group.

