12.10 Sample size calculation

The primary efficacy objective is to show that Nemonoxacin is not inferior to Levofloxacin (Tavanic[®]) for the treatment of CAP, on the basis of the primary efficacy endpoint - clinical success at Visit 4 (Test of cure visit) in the mITT population. The sample size calculation for this endpoint is based on assuming a clinical success rate of 82% in the treatment and in the active control group, and an eligibility of 80% of the randomized patients for mITT population. Non-inferiority margin is chosen to be 15% (i.e., δ = -15%), a one-sided significance level α is set at 5%. Then, to achieve power of 80%, the sample size for equal allocation is estimated as 171 randomized patients in each group (342 patients totally) that provides about 137 patients in each group (274 patients totally) in the mITT population.

Presumably screening of 382 patients will allow enrollment and randomization of 342 patients.

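### The primary Visit 4 comparison is valid but uses no baseline covariate, and the additional logistic regression is unspecified; a pre-specified standardised risk difference against the same -15 point margin would recover some precision.

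*Combined protocol and SAP*

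**What the plan says.** **Primary analysis (12.6.2).** Non-inferiority is judged "by using a one-sided 95% confidence interval for the difference in the primary efficacy endpoint", nemonoxacin minus Tavanic, with the Farrington-Manning method and a limit of -15%, in the mITT population. No covariate or stratum enters.

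**Randomisation (8.5).** Through the IWRS, "each patient will be assigned to one of two treatment groups at the ratio of 1:1". No stratification factor is named. Section 8.6 refers to an IWRS manual for details.

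**Logistic regression (12.6.3).** The whole specification is: "Additionally, the results of statistical comparison of the clinical success rates using the logistic regression will also be provided". It follows the Visit 2 and Visit 3 comparisons and is not tied to Visit 4. Covariates, population and effect measure are not stated.

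**Baseline data (12.4).** They are summarised descriptively and compared between groups by exploratory homogeneity tests. Nothing says what follows if a test shows imbalance.

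**Deferred detail (12.5, 12.9).** Missing-data handling and fuller analysis detail are left to a separate statistical analysis plan, to be final before database close-out.

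**The concern.** The protocol already collects, before treatment starts, variables that its own Appendix 1 uses as markers of severity: age (from date of birth, 10.1.1), oxygen saturation (10.1.4), respiratory rate and temperature (10.3.2) and urea (10.3.5). If these predict cure, a comparison that ignores them has a wider interval than it needs.

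The one planned analysis that could use them is too loosely described to do so. Its covariates could be chosen after the homogeneity tests have been seen, which would weaken any adjusted result. If it is reported as an odds ratio, it cannot be set directly beside a margin that is defined only as a risk difference. At stake are a modest amount of precision in the primary comparison and the usefulness of the supplementary model.

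**Working it through.** **Inputs from the documents (12.10).** The plan rests on "assuming a clinical success rate of 82% in the treatment and in the active control group", a margin of 15 points, one-sided α of 5%, power of 80% and "an eligibility of 80% of the randomized patients for mITT population", giving 171 randomised and about 137 mITT patients per arm (274 in total).

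**Input not in the documents.** The strength of the baseline predictors. It is assumed below and shown as a range.

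**1. The plan's own figure.** With unpooled variance, n = 2 × 0.82 × 0.18 × (1.645 + 0.842)² / 0.15² = 0.2952 × 6.183 / 0.0225 = 81.1, so 82 per arm, or 82 / 0.8 = 102.5, so 103 randomised. The Farrington-Manning formula gives 84 and 105. The stated 137 and 171 are not reproduced. They lie close to one-sided 2.5% with 90% power (138 and 173, unpooled). That is a separate matter for the sponsor to reconcile. Here it matters only because it leaves spare power at the stated α.

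**2. Crude precision and power at 137 per arm.** SE = √(0.2952 / 137) = 0.0464. The one-sided 95% half-width is 1.645 × 0.0464 = 7.6 points. Power at a true difference of zero is Φ(0.15 / 0.0464 − 1.645) = Φ(1.587) = 94.4% (93.9% by Farrington-Manning).

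**3. Gain from adjustment, by simulation.** There were 3,000 trials per scenario, with 137 per arm, 82% success, no treatment effect and four normal covariates. The adjusted estimate was the standardised risk difference from a logistic model. With r the ratio of crude to adjusted variance, the saving is 274 × (1 − 1/r) and the half-width is 7.635 / √r.

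| Assumed c-statistic | r | Patients saved of 274 | Half-width (points) | Reduction (points) |
|---|---|---|---|---|
| 0.63 | 1.016 | 4 | 7.57 | 0.1 |
| 0.71 | 1.091 | 23 | 7.31 | 0.3 |
| 0.77 | 1.124 | 30 | 7.20 | 0.4 |

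A second simulation, with one normal covariate and 1,500 trials per scenario, gave adjusted-to-crude variance ratios of 0.96, 0.92 and 0.84 when the covariate explained 3.6%, 8.7% and 17% of outcome variance (R²). With a useless covariate (R² = 0) the ratio was 1.01, so a poor choice costs almost nothing.

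**4. Effect on power.** Here the variance is multiplied by (1 − R²), with an assumed R² of 5% to 20%.
- True difference 0: power rises from 94.4% to between 95.3% and 97.5%.
- True difference -5 points, variance held at its 82% value: crude power is Φ(0.10 / 0.0464 − 1.645) = Φ(0.509) = 69%. It rises to 71% at R² = 5% and 78% at R² = 20%.
- The ratios in step 3 correspond to R² = 1 − 1/r, which is 1.6% to 11%. On that narrower range, 69% rises to between 70% and 74%.

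**5. Odds-ratio scale.** The odds ratio equivalent to -15 points depends on the control rate.
- At 82%: (0.67 / 0.33) / (0.82 / 0.18) = 0.446.
- At 90%: (0.75 / 0.25) / (0.90 / 0.10) = 0.333.
- At 70%: (0.55 / 0.45) / (0.70 / 0.30) = 0.524.

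Conversely, a fixed odds ratio of 0.446 means -10.0 points at 90% control success and -19.0 points at 70%.

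**The case against.** **The crude test is sound.** Under randomisation the Farrington-Manning comparison is valid, and its interval already allows for chance imbalance. This stands. A reader might infer that imbalance in age or severity biases the primary result. The documents do not support that; the issue is efficiency.

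**The documents never mention an odds ratio.** A reader might infer that the planned regression cannot be read against the margin, or that it is unadjusted. Section 12.6.3 says neither. The effect measure and covariates are unstated, and any logistic model can be standardised to a risk difference. The scale problem is therefore conditional on how the result is reported.

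**Detail may sit elsewhere.** Covariates could be listed in the separate analysis plan, and stratification factors in the IWRS manual. Neither is in the supplied text, so the point concerns what this document specifies.

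**The benefit is small and assumed.** No covariate-outcome association is given. Eligibility narrows the predictors: age is capped at 70, ICU-level disease is excluded (7.1), and raised creatinine is excluded (7.2). The weakest scenario, worth about 4 patients, is therefore plausible. With about 94% power at the stated α, little changes under the planning assumptions. This stands too, and it limits the weight of the point.

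**Not every covariate is shown to be available.** Section 10.2.1 puts the radiologist's conclusion in the source documents and specifies an eCRF category only at Visit 4. A baseline multilobar field cannot be assumed.

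**The adjusted method needs error control at the margin.** Simulated type I error of the standardised estimate at a true difference of -15 points was 4.6% to 5.6% against a nominal 5%, which is acceptable.

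**Conclusion.** The point holds as a missed gain in precision and a gap in specification. The primary analysis needs no correction to be valid. For assumed c-statistics of 0.63 to 0.77 the gain is equivalent to about 4 to 30 of 274 patients, or 0.1 to 0.4 points of a 7.6-point half-width. It is minor if the true difference is zero. It is more useful if nemonoxacin is somewhat worse: at -5 points, power rises from 69% to between 71% and 78% for an assumed R² of 5% to 20%. All these sizes rest on a prognostic strength that the documents do not supply. What needs no assumption is that the logistic model is unspecified and that a raw odds ratio would have no fixed counterpart to -15 points.

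**What to change.** Before database close-out, specify the following for Visit 4 clinical success in the mITT population:

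- A logistic model with treatment and a short fixed list of baseline variables: age, respiratory rate, SaO2 and urea. Add multilobar infiltrate only if its baseline value is confirmed to be in the eCRF.
- Results standardised to a risk difference, with a robust interval at the same one-sided 95% level, read against the same -15 point margin.
- A rule for missing baseline values, fixed in advance.
- The role of the analysis. Preferably it is the primary estimate, with the crude Farrington-Manning result as sensitivity analysis. At the least it is the named key supportive analysis, replacing the open-ended sentence in 12.6.3 and leaving the primary test unchanged.

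The cost is a few sentences of analysis-plan text, a little programming, the missing-value rule and a check of which baseline fields the eCRF holds. No extra data collection is needed for the four core variables.
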